5.3.2 Assessment of Adverse Events

All AEs and SAEs whether volunteered by the patient, discovered by study personnel during questioning, or detected through physical examination, laboratory test, or other means will be reported appropriately. Each reported AE or SAE will be described by its duration (i.e., start and end dates), regulatory seriousness criteria if applicable, suspected relationship to tenecteplase (see following guidance), and actions taken.

To ensure consistency of AE and SAE causality assessments, investigators should apply the following general guideline:

Yes

There is a plausible temporal relationship between the onset of the AE and administration of tenecteplase, and the AE cannot be readily explained by the patient's clinical state, intercurrent illness, or concomitant therapies; and/or the AE follows a known pattern of response to tenecteplase; and/or the AE abates or resolves upon discontinuation of tenecteplase or dose reduction.

No

Evidence exists that the AE has an etiology other than tenecteplase (e.g., preexisting medical condition, underlying disease, intercurrent illness, or concomitant medication); and/or the AE has no plausible temporal relationship to tenecteplase administration (e.g., cancer diagnosed 2 days after first dose of tenecteplase).

Expected adverse events are those adverse events that are listed or characterized in the Package Insert (P.I) or current Investigator Brochure (I.B).

Tenecteplase–Icahn School of Medicine at Mount Sinai
Protocol ML42492

Unexpected adverse events are those not listed in the P.I. or current I.B or not identified. This includes adverse events for which the specificity or severity is not consistent with the description in the P.I. or I.B. For example, under this definition, hepatic necrosis would be unexpected if the P.I. or I.B. only referred to elevated hepatic enzymes or hepatitis.

For patients receiving combination therapy, causality will be assessed individually for each protocol-mandated therapy.

5.4 PROCEDURES FOR ELICITING, RECORDING, AND REPORTING ADVERSE EVENTS

5.4.1 Data Safety Monitoring/CEC

A Data Safety Monitoring Committee/Clinical Events Committee (DSMC/CEC), compiled of 1 neurosurgeon, 1 pulmonologist, and 1 cardiologist, will review safety events throughout the trial. Review of clinical events will be done in a completely blinded fashion. Each event will be reviewed by all DSMC/CEC members and if discrepancy exists in their determinations, then consensus adjudication will be required. The committee will meet to review all Serious Adverse Events (SAEs) and unexpected and related Adverse Events (AEs) every 15 patients. For each 15 patient interval assessment, summary statistics for each cohort will be provided to the DSMC/CEC (after completion of all blinded clinical events review). Following each of these individual case reviews (after analysis/interpretation locked), the DSMC/CEC statistician (who is unblinded, not the study statistician, who will remain blinded) will provide summary data on the ICH's according to cohort. If there is a greater than 2 ICH differential then the study will be halted. Additionally, the DSMC/CEC will be reviewing all enrollments, with summary statistics for each cohort (provided by the DSMC/CEC statistician) after each 15 patients are enrolled. The DSMC/CEC will review SAEs, both related and unrelated, as well as unexpected and related AEs. If a mortality or related serious adverse event occurs, the committee will meet within 72hrs of reporting to review. The committee will have the power to recommend a halt in study enrollment, should there be a safety concern.

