2.3 STUDY OUTCOMES

The following outcomes will be tracked for the trial:

Primary outcome is: the proportion of patients alive and free of respiratory failure (not requiring non-rebreather, high-flow nasal cannula, non-invasive positive pressure ventilation, or mechanical ventilation) at 28 days

- A. Primary safety outcome: Occurrence of intracranial bleeding or major bleeding (Definition: A bleeding episode leading to hemodynamic compromise requiring emergency intervention (such as replacement of fluid and/or blood products, inotropic support, or surgical treatment), or life-threatening or fatal bleeding) within 72 hours of randomization. All outcomes will be assessed in a blinded fashion by the DSMC/CEC.
- B. Secondary outcomes include: 14-day in-hospital mortality, 28-day mortality, ventilator-free days, respiratory failure-free days (not requiring NRB, HFNC, NIPPV, or mechanical ventilation), vasopressor-free days, vasopressor requirements at 24 and 72 hours, P/F ratio at 24 hours and 72 hours, ICU-free days, hospital length of stay, new renal failure, need for renal replacement therapy
- C. Mortality: given a high mortality rate amongst this patient population, patients who die will be included in statistical analysis. Variables of interest will be calculated until the point these patients expire.

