4.2 METHOD OF TREATMENT ASSIGNMENT

This trial will be a randomized, blinded, placebo-controlled trial with an escalating-dose randomized design. Randomization will be completed as follows:

- Block randomization of 2:1 (treatment:control) in blocks of 15, performed twice per dose
- The first block of 15 patients (10 treatment at 0.25 mg/kg dose and 5 placebo control) will be assessed for safety trigger by the DSMC/CEC within 5 working days of the 15th patient completing 72 hours post treatment; if no safety trigger is met (as determined by DSMC/CEC), a second cohort of 15 patients will be enrolled (10 at the 0.25 mg/kg dose and 5 placebo control).
- If no safety trigger occurs after 30 patients enrolled (20 at the 0.25 mg/kg dose and 10 placebo control) then the first cohort 15 patients will be enrolled at the 0.50 mg/kg dose with randomization of 2:1 (treatment:placebo control). If no safety trigger occurs, the last cohort of 15 patients will be enrolled (10 at the 0.50 mg/kg dose and 5 placebo control).
- All SAE's will be reviewed by the DSMC/CEC every 15 patients enrolled and each death will be reviewed within 72 hrs of reporting. Safety trigger is defined as a greater than two patient differential in the occurrence of symptomatic intracranial hemorrhage or major acute bleeding event (defined below) within 72 hours between control and treatment arms.
- Randomization will be stratified according to site.

Tenecteplase and placebo will be provided by Genentech. They will be labeled accordingly indicating which vials contain active drug and which contain placebo. The DCC research pharmacy will de-identify the drugs for distribution to each study center (with tracking of all product) and therefore will remain unblinded to treatment randomization and will be in charge of assigning the correct vials for dosing. Study staff, investigators, and subjects will remain blinded to treatment assignments.

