5.1.1 Stopping Rules

In the case of any Mortality during the 28 day follow up period, enrollment will be halted and DSMC/CEC review will be performed within 72 hrs of notification. The DSMC will then issue a report back to the study PI regarding their recommendation as to re-opening the study or permanently closing the study.

Should there occur, at any time during the study, a difference between the control and treatment cohorts of >2 intracerebral hemorrhages then the study will be halted. Per protocol, the DSMC/CEC will review all ICH's (SAE's). Following each of these individual case reviews (after analysis/interpretation locked), the DSMC/CEC statistician (who is unblinded, not the study statistician, who will remain blinded) will provide summary data on the ICH's according to cohort. If there is a greater than 2 ICH differential then the study will be halted. Additionally, the DSMC/CEC will be reviewing all enrollments, with summary statistics for each cohort (provided by the DSMC/CEC statistician) after each 15 patients are enrolled. They are empowered to halt study enrollment at each of these review points should there be safety concerns. After each of these planned DSMC/CEC reviews the DSMC/CEC will generate a formal report to provide to the study PI.

Tenecteplase–Icahn School of Medicine at Mount Sinai
Protocol ML42492

22

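### ICH counts by arm after each case appear to go to the committee that adjudicates blind, so its later judgement calls are not blinded as stated

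*Combined protocol and SAP*

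**What the plan says.** Section 5.4.1 sets up a single body, the DSMC/CEC, "compiled of 1 neurosurgeon, 1 pulmonologist, and 1 cardiologist, will review safety events throughout the trial". It promises: "Review of clinical events will be done in a completely blinded fashion". Section 2.3 adds, inside the item on the primary safety outcome: "All outcomes will be assessed in a blinded fashion by the DSMC/CEC". No separate adjudication panel is described.

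The same section 5.4.1 says that, once each individual ICH review is locked, the unblinded committee statistician "will provide summary data on the ICH's according to cohort". Sections 5.1.1 and 6.4 repeat this. What cohort means here follows from the halting rule in section 5.1.1, which is triggered by "a difference between the control and treatment cohorts of >2 intracerebral hemorrhages then the study will be halted". The cohorts being compared are therefore the arms.

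A second flow of data runs at the planned reviews: "For each 15 patient interval assessment, summary statistics for each cohort will be provided to the DSMC/CEC", in that case only after the blinded review of events has been completed.

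**The concern.** Blinded adjudication and unblinded monitoring are both normal. The difficulty is that the plan gives both jobs to the same three people and feeds them arm-level ICH counts one case at a time. A count that moves by one after a known patient's case tells the reader which arm that patient is in.

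The lock protects the decision on the ICH just judged. It does not protect what the same members may judge afterwards:

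- relatedness of further SAEs in that patient;
- review of that patient's death, if it occurs;
- later bleeds in that patient. The definition in section 2.3 uses terms that need judgement, such as haemodynamic compromise. The safety trigger in section 4.2 counts major bleeds and symptomatic ICH, so a later bleed after an asymptomatic ICH could still matter to it;
- the next borderline ICH in another patient, judged by members who know the current tally.

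At stake is whether the final report can describe event adjudication as blinded without qualification.

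**Working it through.** **1. Does a per-case table disclose the arm?** Write the cumulative counts before a review as (T, C). A case confirmed as ICH gives either (T+1, C) or (T, C+1), and the table follows each review singly. Subtracting the previous table gives the arm. The first table, 1 v 0 or 0 v 1, needs no subtraction. As a check, all sequences of 1 to 6 ICHs over two arms were enumerated, which gives 1×2 + 2×4 + 3×8 + 4×16 + 5×32 + 6×64 = 642 reviews. The arm was identified correctly in 642 of 642. Before the table, the committee knows only the 2:1 allocation chance. If a case is judged not to be an ICH, the table does not move and nothing is disclosed.

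**2. What does the running tally disclose?** At 2 v 0 with treatment leading, one more treatment-arm ICH gives 3 − 0 = 3, which exceeds 2 and halts the study. If the arms had equal event rates, 2:1 allocation would put the next ICH on treatment with probability 2/3. Members judging that case would know this.

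**3. How many patients?** The only relevant rates in the plan are in section 6.1: 3% and 6%, for major bleeding requiring transfusion or symptomatic ICH. The plan's own figures reproduce:

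- 1 − 0.97^20 = 45.6% (stated: at least 45%);
- 1 − 0.94^20 = 71.0% (stated: at least 70%).

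No rate for ICH alone is given. Using these as an upper stand-in is an assumption. It is not a strict bound, because asymptomatic ICHs may also be reviewed. The rows for 1% and 10% are therefore added as assumed values. With N = 60:

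| Rate p | Expected disclosed, 60p | P(at least one), 1 − (1−p)^60 |
|---|---|---|
| 1% (assumed) | 0.6 | 45.3% |
| 3% (section 6.1) | 1.8 | 83.9% |
| 6% (section 6.1) | 3.6 | 97.6% |
| 10% (assumed) | 6.0 | 99.8% |

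**4. Would fewer tables cure it?** Section 4.2 specifies "Block randomization of 2:1 (treatment:control) in blocks of 15, performed twice per dose", so take 10 treatment and 5 control patients per review. Suppose arm counts were given only then. In a block with at least one event, every event patient's arm is disclosed if all events fall in one arm. With q = 1 − p, that probability is (q^10 + q^5 − 2q^15) / (1 − q^15).

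- 3%: (0.7374 + 0.8587 − 2×0.6333) / 0.3667 = 89.9%
- 6%: (0.5386 + 0.7339 − 2×0.3953) / 0.6047 = 79.7%
- Assumed 1% and 10%: 96.7% and 66.4%

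Interval tables will therefore often disclose arms too. Dropping the per-case tables keeps the adjudicators blind between reviews, but not after each one.

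**The case against.** The strongest reply is that the lock already protects what matters most. Section 6.3 makes the primary safety variable binary per patient: anyone with an intracranial haemorrhage or major bleed is a failure. A patient's arm is disclosed only after the ICH has been confirmed and locked, so that patient already counts as a failure and no later bleed can change it. A reader might infer that blinding is lost for the primary safety comparison itself. The documents do not support that, and this part of the reply stands.

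A reader might also infer that the day-28 efficacy result is assessed by an unblinded committee. The only support is one sentence placed inside the safety item of section 2.3. Section 5.4.1 confines the committee to adverse events, deaths and enrolment. Section 6.2 describes no committee adjudication of the efficacy endpoint, which is survival without the listed respiratory support. Study staff and investigators stay blinded under section 4.2. Bias in such an objective outcome is likely small.

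Nor can it be said that every ICH patient is disclosed well before day 28, because section 6.3 counts events up to that day.

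A further objection is that a yes/no message would hide a 2 v 0 split from a committee expected to use judgement beyond the numerical rule. That is fair, and the committee needs a route to the counts. Finally, an unblinded safety committee is ordinary practice and the trial is not powered for significance (section 3.3). Both are true, but neither makes the blinding statement correct.

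**Conclusion.** The point holds within limits. If the per-case table goes to the DSMC/CEC, as the surrounding text and the halting rule imply, the committee learns the arm of every patient with a confirmed ICH and the running imbalance. Its later judgement calls on those patients, and on the next borderline case, are then not blinded as sections 5.4.1 and 2.3 state. For patients without an ICH, it learns only the imbalance and not the individual's arm.

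On the assumed 3% to 6% rates, about 1.8 to 3.6 of 60 patients would be disclosed, with an 84% to 98% chance of at least one. That is few patients, but a rule set at a difference above 2 turns on few patients. The effect falls on relatedness, death review and later bleeding. It does not fall on the disclosed patient's primary safety result, and it is likely small for death or ventilation. The plan should be changed because the statement and the procedure conflict and the remedy is cheap.

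**What to change.** 1. In sections 5.1.1, 5.4.1 and 6.4, have the unblinded DSMC/CEC statistician apply the existing rule after each locked ICH review and tell the committee only whether the threshold was crossed. Release counts by arm if it is crossed, or if the committee formally requests them for a safety decision. The threshold is unchanged and the study would halt at the same moment. Name the recipient of each report.
2. Keep the 15-patient arm-level reviews on the section 4.2 timeline, after all events reported to date have been locked. Do not wait for day-28 outcomes. The first review falls within 5 working days of the 15th patient reaching 72 hours, and that patient's day 28 comes about 28 − 3 = 25 days after the 72-hour point. Waiting would delay the decision on the next cohort.
3. Because the interval tables will often still disclose the arm of event patients, limit the blinding statements in sections 5.4.1 and 2.3 to events adjudicated before each release of arm-level data. In section 2.3, also say which outcomes the committee assesses.

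The cost is protocol and charter wording, with no extra staff. The downside is that the committee sees arm-level ICH counts later, at the interval review, unless the threshold is crossed or it asks for them.

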6.4 ONGOING SAFETY ANALYSIS

Should there occur, at any time during the study, a difference between the control and treatment cohorts of >2 intracerebral hemorrhages then the study will be halted. Per protocol, the DSMC/CEC will review all ICH's (SAE's). Following each of these individual case reviews (after analysis/interpretation locked), the DSMC/CEC statistician (who is unblinded, not the study statistician, who will remain blinded) will provide summary data on the ICH's according to cohort. If there is a greater than 2 ICH differential then the study will be halted. Additionally, the DSMC/CEC will be reviewing all enrollments, with summary statistics for each cohort (provided by the DSMC/CEC statistician) after each 15 patients are enrolled. They are empowered to halt study enrollment at each of these review points should there be safety concerns. After each of these planned DSMC/CEC reviews the DSMC/CEC will generate a formal report to provide to the study PI.

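### Between the 15-patient reviews, arms are compared on ICH only, so a safety trigger reached through extracranial major bleeding has no specified arm comparison until the next review

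*Combined protocol and SAP*

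**What the plan says.** **The trigger.** Section 4.2: "Safety trigger is defined as a greater than two patient differential in the occurrence of symptomatic intracranial hemorrhage or major acute bleeding event", within 72 hours, between control and treatment arms. Opening the next cohort, and moving to 0.50 mg/kg, depends on this trigger not being met. For the first block, 4.2 says the patients "will be assessed for safety trigger by the DSMC/CEC within 5 working days of the 15th patient completing 72 hours post treatment". For later cohorts it gives no such timing; it requires that no trigger has occurred and sets serious-event review at every 15 patients.

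**Between reviews.** Section 5.1.1 stops the study at any time for "a difference between the control and treatment cohorts of >2 intracerebral hemorrhages then the study will be halted". Section 5.4.1 repeats the rule: "If there is a greater than 2 ICH differential then the study will be halted". Section 6.4 has the same text. In all three, once a case review is locked, the unblinded committee statistician supplies ICH counts by cohort. No other event is named.

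**Other oversight.** Section 5.4.1: "Review of clinical events will be done in a completely blinded fashion". Arm-level information on other events is tied to the scheduled reviews: "For each 15 patient interval assessment, summary statistics for each cohort will be provided to the DSMC/CEC". The committee also meets within 72 hours of a death or a related serious adverse event and may recommend a halt. Any death up to day 28 halts enrollment until it has been reviewed (5.1.1). At the scheduled reviews, 6.4 adds: "They are empowered to halt study enrollment at each of these review points should there be safety concerns". Section 4.2 keeps the trial team blinded: "Study staff, investigators, and subjects will remain blinded to treatment assignments".

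**The concern.** The plan has one definition of unacceptable bleeding for opening the next cohort or dose (ICH or major bleeding) and a narrower one for continuous watching (ICH). Suppose tenecteplase has three extracranial major bleeds and control none: the 4.2 trigger is met and the ICH difference is 0. With two ICH and one extracranial bleed the trigger is again met, and the ICH difference is 2, which is not above 2. In both cases the text allows the rest of the cohort to be enrolled before anyone is directed to compare arms.

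At stake are the remaining patients of that cohort, possibly the first at 0.50 mg/kg, who would receive tenecteplase with heparin after the plan's own bleeding limit had been passed. Section 5.1.2.1 names bleeding as the drug's most common complication, and the combined event is the primary safety outcome (2.3). No section gives a reason for counting only ICH between reviews.

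**Working it through.** **Inputs from the documents.** Four cohorts of 15, each 10 tenecteplase to 5 placebo (4.2). Trigger: D ≥ 3, where D is tenecteplase minus control patients with an event. Event rates of 3% and 6% (6.1). Planned enrollment from June 15 to November 15, 2020 (3.2), or 153 days for 60 patients.

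**Assumptions not in the documents.** The assignment of 6% to tenecteplase and 3% to control; the share *s* of events that are ICH; random order within each block of 15. Section 6.1 states its rates for bleeding requiring transfusion, which is close to the 4.2 event but not identical.

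**Step 1. The plan's own figures.** Chance of at least one event in 20 patients: 1 − 0.97^20 = 45.6% and 1 − 0.94^20 = 71.0%. Section 6.1 says at least 45% and at least 70%, so both reproduce.

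**Step 2. How often the trigger is crossed.** Section 4.2 does not say over which patients the count runs, so three readings are shown at 6% v 3%, from an exact recursion over patients.

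| Count runs over | P(D ≥ 3 at some point) |
|---|---|
| all 60 patients | 34.4% |
| the 30 patients at one dose | 18.4% |
| each cohort of 15 | 6.6% |

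With the trial-wide count, D ≥ 3 is present at a scheduled review in 33.2% of trials, against 34.4% at any time. Nearly all crossings are therefore seen eventually; what is lost is time. For a single cohort counted from zero, the chance of crossing before the 15th patient is only 0.2% (3% in both arms) to 1.4% (6% v 3%). It rises to 14% at an assumed 15% v 3%.

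**Step 3. How often the ICH rule misses the crossing.** If the crossing consists of three tenecteplase events, the ICH rule acts at that moment only if all three are ICH, so the missed share is about 1 − s³: 0.578, 0.875 and 0.984 for s = 0.75, 0.50 and 0.25. Simulation of 300,000 trials gives 0.587, 0.869 and 0.981.

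**Step 4. Further tenecteplase patients after a missed crossing (trial-wide count).** The simulated means are 3.85, 4.06 and 4.16 for the three values of *s*. As a hand check, if the third event is equally likely at each of the ten treated positions in a cohort, the mean number still to come is (0 + 1 + … + 9)/10 = 4.5.

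**Step 5. Allow for the fix's own delay.** 72 hours of observation plus 72 hours to review is 6 days. Accrual is 153/60 = 2.55 days per patient, and 6/2.55 = 2.4, taken as 2 patients. The means fall to 2.86, 2.99 and 3.04.

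**Step 6. Average over all trials, s = 0.50, two-patient lag.**

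- Trial-wide: 0.344 × 0.869 × 2.99 = 0.89, about 0.9 doses. At s = 0.75 it is 0.344 × 0.587 × 2.86 = 0.58; at s = 0.25, 0.344 × 0.981 × 3.04 = 1.03.
- Within dose: 0.36, by direct simulation, about 0.4.
- Restarted each cohort: 0.067 × 0.875 × 1.1 = 0.06, where 1.1 is the simulated mean after the lag.

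At 3% in both arms the three readings give 0.21, 0.07 and 0.01. All of these figures assume that the committee does nothing until the ICH rule acts or the cohort is full, so they are upper bounds.

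**The case against.** The strongest reply is that the plan is tiered on purpose: the combined difference governs cohorts and doses, and an automatic halt at any time is reserved for ICH, the gravest bleed. Major bleeds between reviews also get attention. Under Table 3 an event counts as related unless it meets the criteria for no, so most major bleeds after a thrombolytic would bring a meeting within 72 hours. Deaths halt enrollment. The committee has an unblinded statistician, and nothing forbids it to ask for a split.

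Much of this stands. It rules out the inference that extracranial bleeds go unreviewed, and it is why the exposure figures are upper bounds. It also rules out reading 4.2 as confining assessment to the 15th patient: that timing is written for the first block, without the word only. It does not close the gap. Those meetings rest on blinded case review, and the only arm data specified to follow are ICH counts. Pooled bleeds can raise a general concern but cannot show a difference between arms. Blinded investigators cannot supply the split either.

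A second objection concerns the remedy. The committee also adjudicates outcomes blinded (2.3). With only a few events expected, a running count by arm after each bleed would show it which arm the latest patient was in. This stands, and the fix below is shaped by it.

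**Conclusion.** The gap is real on the text and worth closing, but its expected size is modest. At 6% v 3% the chance that the trigger is crossed at some point is about 34%, 18% or 7% for a count over the trial, within dose or within cohort. With half of events ICH and a two-patient lag, the avoidable exposure is at most about 0.9, 0.4 or 0.06 tenecteplase doses per trial. The arm-specific rates and the ICH share are assumptions, and the documents do not settle which count is meant.

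A reader might infer that a bleeding excess would escape detection, or that 34% and about four further treated patients are the expected harm. Neither is supported. Scheduled reviews would show nearly all crossings. The 34% belongs to the widest of three possible counts, and the four patients are a mean among missed crossings, before any lag and with no earlier action by the committee. Under a per-cohort count at the plan's own rates the effect is close to nil; it would grow if bleeding on tenecteplase were well above 6%. The case for change is earlier action on a limit the plan already has, at little cost.

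**What to change.** Add to 4.2, 5.1.1, 5.4.1 and 6.4:

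> After blinded adjudication of each symptomatic ICH or major acute bleeding event is locked (within 72 hours of reporting, regardless of attribution), the unblinded DSMC/CEC statistician will check the 4.2 differential by arm and tell the committee only whether it exceeds two. If it does, enrollment is paused, the by-arm data are released to the committee, and the committee decides.

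State in 4.2 whether the count runs per cohort, per dose or over the whole trial. Leave the halt for a difference of more than two ICH as it is.

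**Cost.** The statistician, the committee and the step of locking the review before counting already exist for ICH. Expected events are 60 × 0.03 = 1.8 to 60 × 0.06 = 3.6, so about two to four checks, some of which would be done for ICH anyway. Chance pauses rise slightly: with equal rates in both arms and a trial-wide count, an excess of more than two on tenecteplase appears at any time in 8.4% of trials, against 8.0% at reviews only (3% rate), and in 27.1% against 25.2% (6% rate). Most of that comes from using a raw count with 2:1 allocation, which the plan already does. The added check releases by-arm data to the committee only when the threshold is crossed, and study staff stay blinded.
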